6.2. Adverse Events of Clinical Interest and Other Safety Observations

Hemorrhagic events will be identified by hemorrhage Standardized MedDRA Query [SMQ] excluding laboratory terms and be tabulated. Major hemorrhage is a subset of hemorrhagic events which are Grade ≥ 3 or serious or belong to central nervous system (CNS) hemorrhage/hematoma (preferred terms are listed in [Attachment 1](#)).

Other malignancies: are defined as new malignant tumors including solid tumors, skin malignancies and hematologic malignancies and are to be reported for the duration of study treatment and during any protocol-specified follow-up periods including post-progression follow-up for overall survival.

Adverse events of interest and other safety observations will be summarized by treatment arms.

6.3. Deaths

A summary of the number of deaths during the treatment phase and up to 30 days after last dose will be provided, along with the primary cause of death. In particular, frequencies of deaths due to study treatment-related adverse events will also be reported. A death is study medication-related death if the primary cause is a drug related AE.

6.4. Clinical Laboratory Tests

Laboratory data of hematology and serum chemistry up to 30 days after last dose or the end of treatment visit date, whichever is later, will be reported in SI units.

Laboratory results will be graded according to NCI-CTCAE version 4.03 or later. Note that toxicity grading for creatinine increase will be based on the NCI CTC v4.03 or later criteria, but limited only to the part based on the upper limit of normal (ULN), the other part, that is based on change from baseline, will not be used for toxicity grading. Generic normal ranges will be applied whenever reference ranges are not available.

The following laboratory tests will be analyzed:

- Hematology: hemoglobin, platelet count, white blood cell count, absolute neutrophil count, absolute lymphocyte count
- Chemistry: sodium, potassium, blood urea nitrogen, creatinine, aspartate aminotransferase, albumin, alkaline phosphatase, total bilirubin, lactic acid dehydrogenase, uric acid, alanine aminotransferase
- Serum or urine pregnancy testing for young women of childbearing potential only

Descriptive statistics (mean, standard deviation, median, and range) will be calculated for the raw data and for their changes from baseline at each timepoint of assessment as well as for the changes from baseline to the last value. Parameters will be summarized by toxicity grade. Change from baseline to the worst grade during the treatment will be provided as shift tables for selected parameters. In addition, treatment-emergent worsening in toxicity grade will be summarized for selected hematology and chemistry parameters.

The frequencies of abnormal treatment emergent uric acid will be summarized by treatment arm.

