All adverse events will be recorded with the details of the duration and the severity of each episode, action taken with respect to the study drug, investigator's evaluation of its relationship to the study drug (ie, not related, doubtful, possibly, probably, very likely related), and the subjects' outcome. All serious adverse events (life-threatening, results in death, results in or prolongs hospitalization, or results in persistent disability/incapacity, congenital anomaly/birth defect, suspected transmission of any infectious agent, or medically important) must be reported to the sponsor within 24 hours. Progressive disease of NHL should not be reported as an adverse event, but instead, the clinical diagnosis that is associated with disease progression is to be reported.

Adverse Events of Special Interest

Major hemorrhage has been identified as an adverse event of special interest and will require enhanced reporting and data collection (see Section [12.3.3](#), Adverse Events of Special Interest, for details).

Clinical Laboratory Tests

Blood samples for serum chemistry and hematology will be collected. Samples for required laboratory tests may be collected on the day of or day before dosing. For Day 1 Cycle 1 only, clinical laboratory tests do not need to be repeated if the Screening tests were performed within 5 days prior to the first dose of study treatment, with the exception of pregnancy testing which needs to be performed within 24 hours prior to the start of treatment per cycle.

The investigator must review the local laboratory results, document this review, and record any clinically relevant changes occurring during the study in the adverse event section of the CRF. For example, laboratory abnormalities leading to an action regarding any study treatment (dose change, temporary stop, delay of the start of a cycle or permanent stop) or the start of concomitant therapy should be reported. For each laboratory abnormality reported as an adverse event, the following laboratory values should be reported in the laboratory section of the electronic CRF: the value indicative of the onset of each toxicity grade; the most abnormal value observed during the adverse event, and the value supporting recovery to Grade ≤ 1 or to baseline values. The following tests will be performed by the local laboratory at the timepoints shown in the Time and Events Schedule ([Table 1](#), [Table 2](#), [Table 3](#), and [Table 4](#)):

- Hematology Panel
 - hemoglobin

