Laboratory data of hematology, coagulation, and serum chemistry up to 30 days after last dose of study treatment or the End-of-Treatment visit date, whichever is later, will be reported in International System of Units. Laboratory data will be summarized by type of laboratory test. Reference ranges and markedly abnormal results (specified in the Statistical Analysis Plan) will be used in the summary of laboratory data. Descriptive statistics will be calculated for each laboratory analyte at baseline and for observed values and changes from baseline at each scheduled timepoint. Changes from baseline results will be presented in pre- versus posttreatment cross-tabulations (with classes for below, within, and above normal ranges). Frequency tabulations of the abnormalities will be made. A listing of subjects with any laboratory results outside the reference ranges will be provided. A listing of subjects with any markedly abnormal laboratory results will also be provided.

Parameters with predefined NCI-CTCAE toxicity grades will be summarized. Change from baseline to the worst adverse event grade experienced by the subject during the study will be provided as shift tables.

Electrocardiogram (ECG)

The effects on cardiovascular variables will be evaluated by means of descriptive statistics and frequency tabulations. These tables will include observed values and changes from baseline values (the initial ECG will be used as baseline).

Physical Examination

Physical examination findings will be summarized at each scheduled timepoint. Descriptive statistics will be calculated at baseline and for observed values and changes from baseline at each scheduled timepoint. Frequency tabulations of the abnormalities will be made.

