12.1.3. Severity Criteria

An assessment of severity grade will be made using the NCI-CTCAE, Version 4.03. The investigator should use clinical judgment in assessing the severity of events not directly experienced by the subject (eg, laboratory abnormalities).

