17.2.2. Required Prestudy Documentation

The following documents must be provided to the sponsor before shipment of study drug to the study site:

- Protocol and amendment(s), if any, signed and dated by the principal investigator
- A copy of the dated and signed (or sealed, where appropriate per local regulations), written IEC/IRB approval of the protocol, amendments, ICF, any recruiting materials, and if applicable, subject compensation programs. This approval must clearly identify the specific protocol by title and number and must be signed (or sealed, where appropriate per local regulations) by the chairman or authorized designee.
- Name and address of the IEC/IRB, including a current list of the IEC/IRB members and their function, with a statement that it is organized and operates according to GCP and the

applicable laws and regulations. If accompanied by a letter of explanation, or equivalent, from the IEC/IRB, a general statement may be substituted for this list. If an investigator or a member of the study-site personnel is a member of the IEC/IRB, documentation must be obtained to state that this person did not participate in the deliberations or in the vote/opinion of the study.

- Regulatory authority approval or notification, if applicable
- Signed and dated statement of investigator (eg, Form FDA 1572), if applicable
- Documentation of investigator qualifications (eg, curriculum vitae)
- Completed investigator financial disclosure form from the principal investigator, where required
- Signed and dated Clinical Trial Agreement, which includes the financial agreement
- Any other documentation required by local regulations

The following documents must be provided to the sponsor before enrollment of the first subject:

- Completed investigator financial disclosure forms from all subinvestigators
- Documentation of subinvestigator qualifications (eg, curriculum vitae)
- Name and address of any local laboratory conducting tests for the study, and a dated copy of current laboratory normal ranges for these tests, if applicable
- Local laboratory documentation demonstrating competence and test reliability (eg, accreditation/license), if applicable

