6.4.1. Creatinine Clearance

Creatinine clearance (CrCl) is calculated using Schwartz's formula:

$$\text{CrCl} = \frac{(k * \text{Ht})}{\text{Cr}_{\text{serum}}}$$

Note: K = 0.55 for girls and boys \leq 10yrs

K = 0.70 for boys $>$ 10yrs

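### SAP 6.4 grades creatinine only against the ULN, and no laboratory output with stated criteria counts subjects by the size of the rise over their own baseline value

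*SAP*

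**What the plan says.** SAP 6.4 grades laboratory results by CTCAE version 4.03 or later, with one exception. For creatinine increase only the ULN part of the criteria applies: "the other part, that is based on change from baseline, will not be used for toxicity grading".

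The other planned outputs that could show a creatinine rise are these:

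- **SAP 6.4, grade tables.** Parameters are summarised by grade. "Change from baseline to the worst grade during the treatment will be provided as shift tables for selected parameters". Worsening in grade on treatment is also summarised for selected hematology and chemistry parameters. The SAP does not say whether creatinine is among the selected parameters.
- **SAP 6.4, change statistics.** Means, standard deviations, medians and ranges of the values and of their changes from baseline.
- **SAP 6.4.1.** "Creatinine clearance (CrCl) is calculated using" the Schwartz formula. No table, cut-off or change from baseline is attached to it.
- **Protocol 11.7.** "Parameters with predefined NCI-CTCAE toxicity grades will be summarized". Pre- versus posttreatment results go into "cross-tabulations (with classes for below, within, and above normal ranges"), and subjects with values outside the reference range are listed. Markedly abnormal results are also to be listed, with the criteria left to the SAP; SAP 6.4 gives none.

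Outside the laboratory tables, protocol 9.8 tells the investigator to "record any clinically relevant changes occurring during the study in the adverse event section of the CRF". Protocol 12.1.3 governs the severity of adverse events: "An assessment of severity grade will be made using the NCI-CTCAE, Version 4.03".

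**The concern.** A ULN-only grade depends on where a subject's value ends, not on how far it has moved. A subject who starts well below the ULN can double or triple creatinine and remain ungraded. The protocol's general plan to summarise CTCAE laboratory grades does not contain this limit. The SAP adds it without giving a reason and without an entry in SAP section 9, which is reserved for changes to protocol-specified analyses.

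Safety and tolerability in pediatric subjects and young adults is a secondary objective of Part 2, which enrolls from age 1. At stake is the sensitivity of one descriptive laboratory summary: a rise that is large for the subject, stays within range and is not reported as an adverse event would not be counted in any table whose criteria are written down.

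**Working it through.** The plan states no figure on this point, so there is nothing to reproduce. The check has two parts.

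**1. When does a rise go ungraded?**

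Inputs: the ULN-only rule (SAP 6.4) and the clearance formula CrCl = k x height / serum creatinine (SAP 6.4.1). Assumption: the lowest ULN-based grade starts just above the ULN. The CTCAE table itself is not in the documents.

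Let baseline = f x ULN and let creatinine rise r-fold. The new value is r x f x ULN, so there is no grade when r x f <= 1, that is, when f <= 1/r. At fixed height and k, clearance after divided by clearance before is 1/r, a fall of 1 - 1/r, with no ULN term.

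| Fold rise r | Ungraded when f is at or below 1/r | Fall in CrCl, 1 - 1/r |
|---|---|---|
| 1.5 | 0.67 | 33% |
| 2 | 0.50 | 50% |
| 3 | 0.33 | 67% |

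Check around the doubling threshold: 2 x 0.50 = 1.00 x ULN (no grade); 2 x 0.51 = 1.02 x ULN (graded).

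Read the other way, the fold rise a subject must exceed to be graded is 1/f. The documents do not give f, so this is a range for illustration:

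| f (baseline / ULN) | 1/f |
|---|---|
| 0.3 | 3.3 |
| 0.4 | 2.5 |
| 0.5 | 2.0 |
| 1.0 | 1.0 (no gap) |

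The result depends only on baseline relative to the ULN, so it holds with a correct local ULN too. Protocol 17.2.2 requires sites to supply "a dated copy of current laboratory normal ranges for these tests, if applicable".

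**2. Does another planned laboratory output count such a subject?**

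- *Grade summary, shift and worsening tables.* For creatinine these inherit the ULN-only grade. The subject has no grade at baseline and none at worst.
- *Normal-range cross-tabulation.* The subject never reaches the above-range class.
- *Out-of-range listing.* A post-baseline value that ends within range does not enter it.
- *Change-from-baseline statistics.* These are pooled by group. Even the range need not reveal the case: a doubling from 0.3 x ULN is a raw change of 0.3 x (2 - 1) = 0.3 ULN, smaller than the 1.0 x (1.5 - 1) = 0.5 ULN of a 1.5-fold rise from 1.0 x ULN.
- *Creatinine clearance.* It would fall by half on a doubling, whatever the ULN, but no output is stated for it.
- *Markedly abnormal listing.* With no criteria in SAP 6.4, one cannot tell whether it would capture the subject.

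No output with stated criteria counts subjects by the size of the rise.

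**The case against.** **Several tables do compare each subject with baseline.** This stands. The shift tables, worsening summary and cross-tabulations each set a subject's on-treatment category against that subject's own baseline category. A reader might infer that the plan makes no within-subject comparison at all; the documents do not support that. What is missing is a count by size of rise, because for creatinine those categories rest on the ULN or the normal range.

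**Adverse event reporting is a separate route.** This also stands. Protocol 9.8 requires clinically relevant laboratory changes to be recorded as adverse events, naming those that lead to a change, stop or delay of treatment or to concomitant therapy. It also asks for the values at onset of each grade and at worst. Protocol 12.1.3 then grades the event with no ULN-only limit. So it would be wrong to infer that a doubling goes unreported. What can be missed is a within-range rise that led to no action and was not judged clinically relevant.

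**The rule is an explicit, prespecified choice.** Protocol section 11 leaves specific details to the SAP, and protocol 12.1.3 concerns adverse events rather than laboratory grading. Reading SAP 6.4 as a contradiction of the protocol goes too far; it is a narrowing. The choice can be defended: baseline is a single last pre-dose value (SAP 2.6 and 6), so one low reading inflates a fold change.

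**No size has been shown.** It is tempting to infer that young children in particular will be missed. The documents give no baseline creatinine by age. Protocol 4.1 refers to a ULN for age at eligibility, which weakens that inference, and it admits some subjects with baseline above the ULN, for whom this gap does not arise. The number affected is unknown.

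These points limit the priority. They do not supply the missing count.

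**Conclusion.** The point holds in limited form. With ULN-only grading, a doubling of creatinine from at or below 0.5 x ULN gets no laboratory grade, and no other laboratory output with stated criteria counts subjects by fold rise over baseline. This rests on one assumption, that ULN-based grading starts above the ULN. The thresholds are exact given that assumption; how often subjects fall below them cannot be estimated from the documents.

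The consequence is small. SAP section 6 plans no inferential statistics for safety, the rule is the same in both arms, and the primary endpoint and efficacy conclusion are untouched. This is a low-priority gain in the sensitivity of one safety summary, not a threat to the trial's conclusions.

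**What to change.** In SAP 6.4, keep the ULN-based creatinine grades and add one descriptive table by treatment arm: the number and percent of subjects whose worst creatinine, from first dose to the end of the SAP 6.4 laboratory window (30 days after last dose or the end-of-treatment visit, whichever is later), is at least 1.5, 2 and 3 times their own baseline. Optionally, also summarise by arm the worst creatinine clearance from SAP 6.4.1 as a percent of baseline.

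Cost: one sentence in the SAP and one table from creatinine values already collected. No new data and no effect on alpha are involved, and it remains feasible although enrollment has stopped (protocol 11.9.1). Downside: some transient rises from a low single baseline value will be flagged, so a table footnote should say that a count here is not a CTCAE grade.

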6.4.1. Creatinine Clearance

Creatinine clearance (CrCl) is calculated using Schwartz's formula:

$$\text{CrCl} = \frac{(k * \text{Ht})}{\text{Cr}_{\text{serum}}}$$

Note: K = 0.55 for girls and boys \leq 10yrs

K = 0.70 for boys $>$ 10yrs

6.5. Electrocardiogram

QT prolongation and other clinically significant ECG abnormalities will be summarized and listed. Descriptive statistics will be calculated for the ECG parameters at baseline.

The ECG parameters that will be summarized are heart rate, RR interval, QT interval, and QTc. The QTc will be computed using Bazett's correction, ie, $QTc_B = QT / \sqrt{RR}$, and Fridericia's correction, ie, $QTc_F = QT / \sqrt[3]{RR}$.

All treatment-emergent abnormal findings will be tabulated, displaying the number of subjects with abnormal findings after dosing up to the end (Day 28) of the last cycle. An abnormal finding is considered to be treatment-emergent if it occurred during treatment and up to 30 days after the last dose.

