1.3. Ibrutinib

1.3.1. Nonclinical Studies

Pharmacologic Profile

In vitro studies have shown that ibrutinib binds covalently to a cysteine residue (Cys-481) in the BTK active site, leading to potent and irreversible inhibition of BTK enzymatic activity.³⁰ Ibrutinib inhibited the proliferation of cell lines derived from patients with DLBCL, with a median effective concentration of 1 or 2 nM.

Toxicology

General toxicity studies in rats and dogs have identified lymphoid tissues (lymphoid depletion) and the gastrointestinal tract (soft feces/diarrhea, with or without inflammation) as the target organs with potential relevance to human safety. Results from an immunotoxicity assessment of ibrutinib in rats were consistent with the expected pharmacology of the drug and included dose-associated decreases in B-lymphocyte numbers, lymphoid depletion in the white pulp of the spleen and decreased immunoglobulin responses to keyhole limpet hemocyanin immunization. Cardiovascular assessments in dog safety pharmacology and toxicity studies identified decreased heart rate and prolonged PR intervals related to ibrutinib administration as a relevant finding.

Pharmacokinetics and Metabolism

After oral administration, ibrutinib showed rapid absorption and high plasma clearance in nonclinical species. Excretion of ibrutinib-related radioactivity occurred principally via feces. In human plasma, 97.3% of ibrutinib and 91.0% of the major dihydrodiol metabolite PCI-45227 was bound to protein.

In vitro nonclinical data show that ibrutinib is metabolized primarily by cytochrome P450 (CYP)3A. Ibrutinib is a weak reversible inhibitor toward CYP2B6, CYP2C8, CYP2C9, CYP2C19, CYP2D6, and CYP3A4/5 and does not display time-dependent CYP450 inhibition. The dihydrodiol metabolite of ibrutinib is a weak inhibitor toward CYP2B6, CYP2C8, CYP2C9, and CYP2D6. Both ibrutinib and the dihydrodiol metabolite are at most weak inducers of CYP450 isoenzymes in vitro.

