 - platelet count
 - white blood cell count
 - absolute neutrophil count
 - absolute lymphocyte count
 - lymphoblasts (also called blasts) if applicable
- Serum Chemistry Panel
 - sodium
 - potassium
 - blood urea nitrogen or urea
 - creatinine
 - aspartate aminotransferase
 - albumin
 - alkaline phosphatase
 - total bilirubin
 - lactic acid dehydrogenase
 - uric acid
 - alanine aminotransferase
- Viral Serology Panel
 - HBsAg
 - HBsAb
 - HBcAb
 - Hepatitis C
 - HIV

If Hepatitis B core antibody is positive, Hepatitis B DNA by polymerase chain reaction (PCR) needs to be performed and confirmed as negative to continue with study participation. Subjects should be monitored for viral reactivation by liver enzymes and Hepatitis B PCR when appropriate and prophylactic antiviral medication should be considered per local practice.

- Tetanus and pneumococcal antibody titers (central laboratory)
- Serum or urine pregnancy testing for young women of childbearing potential only

Electrocardiogram/Echocardiography/MUGA Scan

Baseline LVEF/SF must be assessed by MUGA or echocardiogram and demonstrate LVEF $\geq 50\%$ or SF $> 28\%$ for subjects to be eligible and may be repeated throughout the study, protocol directed or when clinically indicated. When the examination is repeated, the same modality should be used. Echocardiography/MUGA and 12-lead ECGs will be obtained for all subjects at the timepoints specified in the Time and Events Schedule ([Table 1](#), [Table 2](#), and [Table 3](#)). Additional cardiovascular assessments should be performed as clinically appropriate to ensure subject safety.

During the collection of ECGs, subjects should be in a quiet setting without distractions (eg, television, cell phones). Subjects should rest in a supine position for at least 5 minutes before ECG collection and should refrain from talking or moving arms or legs. If blood sampling is scheduled for the same timepoint as ECG recording, the ECG should be performed before the blood draw.

Vital Signs

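### SAP 6.5 leaves PR (and QRS) out of the quantitative ECG summary and states ECG descriptive statistics only at baseline, so a sub-threshold PR shift would not be quantified

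*SAP*

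**What the plan says.** The Toxicology text of Protocol 1.3.1 states that cardiovascular assessments in dogs "identified decreased heart rate and prolonged PR intervals related to ibrutinib administration as a relevant finding". Protocol 2.1.2 makes intensified cardiac monitoring part of the Part 2 safety endpoint. Protocol 9.8 provides the tracings: "Echocardiography/MUGA and 12-lead ECGs will be obtained for all subjects at the timepoints specified".

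For the analysis, Protocol 11.7 says: "The effects on cardiovascular variables will be evaluated by means of descriptive statistics and frequency tabulations". It does not name the variables, but it does say what the tables hold: "These tables will include observed values and changes from baseline values (the initial ECG will be used as baseline".

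SAP 6.5 is narrower on both counts. On variables: "The ECG parameters that will be summarized are heart rate, RR interval, QT interval, and QTc", with QTc by Bazett and Fridericia. On time points: "Descriptive statistics will be calculated for the ECG parameters at baseline". It adds two further outputs: "QT prolongation and other clinically significant ECG abnormalities will be summarized and listed", and "All treatment-emergent abnormal findings will be tabulated, displaying the number of subjects with abnormal findings". SAP 9, which is meant to record changes to the protocol's analyses, has no text under its heading.

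**The concern.** The protocol's toxicology section names two ECG effects of the drug. The SAP list covers heart rate twice, since RR in seconds is 60 divided by heart rate, and does not cover PR at all. The other listed parameters, QT and QTc, describe repolarisation, for which that section gives no signal.

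An interval effect can show as a shift in the average before individual tracings are called abnormal. Summaries of values and changes by arm would show such a shift; counts of abnormal findings would not. At stake is the descriptive record of cardiac safety in children and young adults, in a trial where cardiac monitoring after anthracycline exposure is singled out and one of the two backbones, RVICI, contains idarubicin.

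**Working it through.** The omission is established by comparing texts. The precision figures at the end are illustrative.

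**1. Parameters.**

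| ECG effect named in Protocol 1.3.1 (dogs) | In the SAP 6.5 list? |
|---|---|
| Lower heart rate | Yes, as heart rate and as RR |
| Longer PR interval | No |

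QRS is also not listed.

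**2. Time points.** Protocol 11.7 gives observed values and changes from baseline. The only time point SAP 6.5 attaches to descriptive statistics is baseline. This affects heart rate, QT and QTc as well, so adding PR to the list alone might produce only a baseline row.

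**3. What the other outputs would catch.**
- The clinically significant abnormalities and the treatment-emergent abnormal findings in SAP 6.5 are not limited to the listed parameters. A long PR or an AV block judged abnormal would appear.
- SAP 6.1.1 summarises every treatment-emergent adverse event by preferred term, so a reported conduction disorder would appear.
- All of these are counts above a threshold. None gives the mean PR, its change, or a difference between arms.
- The abnormal-findings table carries two windows: to Day 28 of the last cycle, and to 30 days after the last dose. Protocol 9.1.3 places the End-of-Treatment visit after progression within 30 days of the last dose, so that ECG can fall inside one window and outside the other.

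**4. How many ECGs there would be.** In Part 2, Protocol Table 2 (footnote f) schedules Treatment Phase ECGs at Screening and End-of-Treatment for all subjects, and at the end of each cycle for RVICI only. Table 3 adds one at the end of ibrutinib monotherapy if none was done in the previous 30 days.

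**5. Illustrative precision for an arm difference in mean PR change.** Inputs: 48 versus 24 subjects (from 72 at 2:1, Protocol 11.2), and an SD of change of 10, 15 or 20 ms. The SD is an assumption; the documents give none.

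SE = SD × √(1/n₁ + 1/n₂); 90% half-width = 1.645 × SE.

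Enrollment stopped after the interim analysis (Protocol 11.9.1), and the number randomised is not stated. Taking the 46 subjects projected for the interim in Protocol Table 11, 2:1 gives 46 × 2/3 ≈ 31 versus 15, also an assumption.

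- 48 versus 24: √(1/48 + 1/24) = √0.0625 = 0.250
- 31 versus 15: √(1/31 + 1/15) = √0.0989 = 0.315

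| SD (ms) | SE, 48 v 24 | Half-width | SE, 31 v 15 | Half-width |
|---|---|---|---|---|
| 10 | 2.50 | ±4.1 | 3.15 | ±5.2 |
| 15 | 3.75 | ±6.2 | 4.72 | ±7.8 |
| 20 | 5.00 | ±8.2 | 6.29 | ±10.3 |

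All rows assume a paired ECG for every subject; missing End-of-Treatment tracings would widen them. No power figure is given, because SAP 6 plans no inferential statistics on safety data.

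**The case against.** The strongest reply is that the SAP already covers what matters clinically. Abnormal ECG findings of any kind are tabulated and conduction disorders are reported as adverse events. In Part 1, the Study Evaluation Team reviews cardiac rhythm abnormalities in RVICI subjects (Protocol 11.10). This stands. A reader might infer from the missing PR row that a conduction effect in children would go unseen; SAP 6.5 and 6.1.1 do not support that.

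Second, the PR finding is in dogs. The clinical text on cardiac arrhythmias in Protocol 1.3.2.2 names atrial fibrillation, atrial flutter and ventricular tachyarrhythmia, not PR prolongation. This also stands: the documents do not say that ibrutinib prolongs PR in humans.

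Third, the schedule limits what a PR summary could show. RICE subjects have one scheduled Treatment Phase ECG after Screening, and no ECG is timed to dosing. The End-of-Treatment visit may come days or weeks after the last dose, against a mean half-life of 4.3 to 8.9 hours (Protocol 1.3.2.1). RVICI end-of-cycle ECGs fall within 3 days before the next cycle, close to lumbar punctures for which Protocol 4.3 stops ibrutinib 24 hours beforehand. On-drug and off-drug tracings would be mixed. A reader might infer that adding PR would confirm or rule out an effect; it would not.

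Finally, SAP 6 says in general terms that descriptive statistics are reported for all safety data, which might be read to include post-baseline ECG values. That sentence names no parameter or time point. It does not put PR on the list in 6.5, nor does it settle the conflict with Protocol 11.7.

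**Conclusion.** The point holds in a limited form. SAP 6.5 leaves out of its quantitative summary one of the two ECG effects that the protocol's toxicology section calls relevant, and it states a narrower set of time points than Protocol 11.7. A PR shift that stays below the thresholds for an abnormal finding, a clinically significant abnormality or an adverse event would not be quantified.

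This affects a descriptive safety table, not the primary endpoint or any tested hypothesis, and correcting it is a cheap improvement. What would be gained is an estimate of the arm difference to within roughly ±4 to ±10 ms, given the assumed SD and the two sample sizes above, with the limits on timing already described. The case for the change rests on the mismatch between the documents, not on those figures.

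**What to change.** In SAP 6.5:

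1. Change the parameter list to: heart rate, RR interval, PR interval, QRS duration, QT interval and QTc. RR stays because both QTc formulas use it.
2. Replace the baseline-only sentence with descriptive statistics by treatment arm, for observed values and changes from baseline, at each scheduled ECG and for all listed parameters, in line with Protocol 11.7.
3. Keep the analysis descriptive, with no test and no power claim. State beside the table that RICE subjects have Treatment Phase ECGs only at Screening and End-of-Treatment and that tracings are not timed to dosing.

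The cost is SAP wording and a few extra table rows. No new procedure is needed, since 12-lead tracings are already scheduled. The documents do not say whether the CRF records PR and QRS; if it does not, they would have to be entered retrospectively from the tracings.
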